#### **4.2.3. Study Participant Characteristics**

The patient's age, sex, race (Non-Japanese and Japanese), weight, height, smoking habits, APOE4 status, MMSE baseline value, FCSRT-IV total score, CDR-Sum of Boxes score, ADAS-Cog (14), NTB total score, and ADL24, number of ARIA-E, ARIA-M and/or other demographic characteristics will be summarize in baseline table for all IV dose group and subset by Part A Single IV doses, Part B Multiple doses (Q2W dosing), and Part C Chronic doses (Q4W dosing). The placebo-groups will be combined within the 3 study Parts (A,B, and C). In addition, a baseline table will be constructed for all Japanese patients and a similar baseline summary table will constructed for all non-Japanese patients. A complete patient listing of the baseline characteristics will be constructed for each IV dose group.

#### **4.2.4. Pharmacokinetic Analyses**

##### **4.2.4.1. Pharmacokinetic Parameter Estimation**

The analysis methodology of PK parameter estimates for LY3002813 are documented in a separate PK analysis plan.

#### **4.2.5. Pharmacodynamic Analyses**

Pharmacodynamic and cognition measures as function of visit or time relative to first IV dose will be summarized and/or plotted as appropriate. As there will not be sufficient information to make informative comparisons on the Japanese population, all analyses will be conducted on the overall population unless otherwise specified. As the analyses are considered exploratory, changes to the planned analyses will not require a protocol amendment. The following sections provide details of the specific pharmacodynamic measure or cognitive measure.

##### **4.2.5.1. Primary Objective of Amyvid PET Imaging Statistical Analyses**

Statistical assessment of the composite SUVr change from baseline will be analyzed by a mixed model repeated measure (MMRM). The response measurements are (1) SUVr change from baseline and (2) the percent change from baseline. Baseline is defined as the pre-dose SUVr obtained at screening visit 3 or prior to randomization. The change from baseline are computed from the SUVr obtained from the scheduled study visits at weeks 12, 24, 36, and 48. Patients have the option to have a PET image taken at early discontinuation. In those case, SUVr value will be mapped to the closest scheduled study visit at weeks 12, 24, 36, or 48. The planned analyses is an MMRM using an appropriate covariance structure with fixed effects of treatment doses (LY3002813 and placebo), study visit, and interaction between treatment and visit. A baseline covariate adjustment may be used. The primary comparison is between LY3002813 IV doses and placebo for change from baseline in composite SUVr or percent change in composite SUVr at last PET imaging visit. This analysis may be repeated for individual brain regions of SUVr if needed. A table of the LSmeans per dose group with associated p-value contrast to placebo will be constructed. A graphical summary of the LSmeans and a mean confidence interval on the y-axis and the study visit on the x-axis for each IV dose-group. Given the small sample size of n=6 patients per IV dose group, simplification of the mixed-effects model might be considered if the model fails to converge or other model fit diagnostics.

In addition to the MMRM analysis, a Bayesian posterior probability may be computed for each LY3002813 dose compared to placebo. For each dose, the credible interval will be computed for each dose relative to placebo. This analysis may be omitted if access to appropriate software such as SAS version 9.4 is not available.

Summary tables for SUVr values across the PET scan study visits for each IV dose group will include the n, mean, median, SD, minimum, maximum values. In addition, the number of patients within each IV dose group and study visit with post-dose composite SUVr values less than 1.2.

In addition to Amyvid PET scan SUVr analysis, an exploratory analysis of 18F-AV-1451 PET scan SUVr results will be conducted using an analysis of covariance (ANCOVA) model. The

18F-AV-1451 PET scans will be obtained from each randomized patient at pre-dose Visit 4 and at Visit 17 approximately 72 weeks post-dose. The change in SUVr as the response variable and the IV dose group as the explanatory factor with the baseline SUVr as a covariate. The primary contrast will be the mean change in SUVr of each IV dose group relative to placebo. A summary table of the LSmean results and contrast p-value will be generated. In addition, a graphical display of the LSmean and confidence interval on the y-axis and the IV dose-groups and placebo along the x-axis.

Magnetic resonance imaging changes in volume over the course of the study will be explored, and exploratory evaluation of whole brain and anatomically localized structural changes will be summarized (including, but not limited to, whole brain, ventricle, and hippocampus). Magnetic resonance imaging volumetric assessments will be obtained at baseline, 24 weeks, 48 weeks, and 72 weeks as applicable. An MMRM will be constructed by fitting treatment and study visit as fixed effects. Response variables are brain structural changes of whole brain, ventricle, and hippocampal volumes.

Additionally, the relationship between LY3002813 serum exposure and imaging endpoints may be explored graphically or by additional exploratory analyzes.

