Part C (Cohorts 6 and 7): 19 doses of LY3002813 or placebo administered Q4W for 72 weeks followed by 12-weeks follow-up

Criteria for Evaluation:

Safety: Safety parameters that will be assessed include AEs, concomitant medications, cognitive function, physical and neurological examinations, vital signs, electrocardiogram, safety laboratory values, and MRI scans.

Bioanalytical: Serum and CSF samples will be used to determine concentrations of LY3002813. Serum and CSF concentrations of LY3002813 will be determined by validated enzyme-linked immunosorbent assay.

Pharmacogenomics: A blood sample will be used to test for genetic variants that may influence response to treatment.

Pharmacokinetic/Pharmacodynamic: Blood and CSF samples will be used to determine the concentrations of LY3002813. Cortical standardized uptake value ratio (SUVr) from florbetapir and 18F-AV-1451 positron emission tomography scans will be analyzed to estimate mean change. The CSF results from the lumbar punctures taken pre- and postinfusion will be analyzed to estimate the mean change from preinfusion. The dependent variables are $\text{A}\beta_{1-40}$, $\text{A}\beta_{1-42}$, total tau, and phospho-tau.

Statistical Evaluation Methods:

Up to approximately 150 patients may be enrolled to ensure that a minimum of approximately 72 patients complete the study. The sample size is customary for studies evaluating safety, PK, and/or PD parameters; at the conclusion of the trial, confidence intervals for PK, PD, and cognition endpoints may be computed in order to evaluate the precision of the estimates where appropriate. In addition, based on prior Lilly clinical trials, 6 patients randomized to each LY3002813 dose and placebo provide over 90% power to detect at least a 17% mean florbetapir SUVr reduction of a dose compared to placebo without multiple comparison adjustment.

Statistical: PK/PD analyses will be conducted on the full analysis set. This set includes all data from all randomized patients receiving at least 1 dose of the investigational product according to the treatment the patients actually received. Safety analyses will be conducted for all enrolled patients, whether or not they complete all protocol requirements. A model-based approach of analysis will be used. Summary statistics, data tabulations, and data graphs by ethnicity (Japanese and non-Japanese) will be provided as appropriate.

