5.2. Rationale and Justification for the Study

This is the second study with LY3002813 in patients with MCI due to AD or mild to moderate AD. Data from Study AACC indicated a dramatic reduction in cerebral amyloid (as assessed by florbetapir PET imaging) in the 6 patients who received 3 to 5 doses of 10 mg/kg of LY3002813 IV over 6 months, without cerebral vasogenic edema or microhemorrhage complications in this dose group. These positive results were accompanied by a high incidence of ADAs at all doses, as well as infusion reactions noted at doses ≤ 3 mg/kg. Dosing was stopped in the multiple-dose phase of Phase 1 Study I5T-MC-AACC (Study AACC) due to high prevalence of ADAs and unexpected rapid clearance of the study drug.

As a result of the significant target engagement (amyloid reduction by florbetapir PET) that was identified after 3 to 5 doses of LY3002813 10 mg/kg IV over 6 months, the current study is proposed to determine whether different dosing regimens (single-dose, short-term “induction” dosing with higher, more frequent dosing; and chronic dosing for maximal PD effect) can mitigate immunogenicity and immune safety issues, and produce sustained amyloid reduction. The aims of the study are to evaluate the effect of different dosing regimens on ADAs and amyloid plaque removal, and assess the relationship between PK, PD (amyloid removal), immunogenicity, and clinical safety. As a high prevalence of ADAs was observed in Study AACC, a risk management plan for immune safety will be incorporated into the clinical trial including at least 6 hours monitoring after completion of each infusion, a protocol for management of infusion reactions, and standardized data collection for infusion reaction AEs.

A favorable risk/benefit profile and dosing selection will support further development of LY3002813, including: (1) removal of amyloid consistent with Study AACC; (2) persistence of amyloid removal after completion of dosing; (3) acceptable clinical impact of ADAs; (4) manageable risk of clinically significant infusion reactions; and (5) low incidence of amyloid-related imaging abnormalities-edema (ARIA-E) and ARIA-H.

6. Objectives

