Cohort 2 will only be initiated after review of safety data from Cohort 1. Thereafter, Cohort 3 will be initiated after review of safety data from Cohort 2. Cohorts 4 and 5 will be initiated after review of safety and PK data from their respective single-dose cohorts. An additional requirement for Cohort 5 is confirmation that at least 2 patients have received at least 3 doses each of LY3002813 safely in Cohort 4. Cohort 6 and Cohort 7 may proceed in parallel with Cohorts 4 and 5, respectively. In addition, Cohort 7 will only be initiated after confirmation that at least 2 patients have received at least 2 doses each of LY3002813 safely in Cohort 6.

Safety/PK reviews will occur after a minimum of 4 patients receiving LY3002813 and 1 patient receiving placebo have been dosed. For Cohorts 1 to 3, no more than 1 patient will be dosed on any one particular day. For Cohorts 4 to 7, patients dosed on the same day at any one site should not be dosed simultaneously but should be separated by at least 1 hour. Each cohort will contain approximately 6 (single dose) or 9 (multiple dose) patients treated with LY3002813 and 2 to 3 patients treated with placebo so that the study can detect target engagement and ADA frequency relative to those observed in Study AACC.

The primary target engagement outcome is the reduction of cerebral amyloid as measured by quantitative amyloid PET imaging (florbetapir SUV_r) assessed at baseline and at 12 weeks, 24 weeks, 36 weeks, 48 weeks, and 72 weeks after starting treatment. The early postbaseline scans are aimed to assess the time course of amyloid reduction; the later scans are aimed to assess sustainability of amyloid reduction after completion of dosing in Parts A and B, and maximal amyloid removal in Part C.

Safety and PK of LY3002813 will be assessed throughout the study for each cohort. In addition, blood samples for the assessment of immunogenicity will be taken at regular intervals throughout the dosing and follow-up periods. For Cohorts 1 through 3, a CSF sample will be taken by single lumbar puncture (LP) at baseline, another approximately 3 days after dosing to measure the CSF concentration of LY3002813 and CSF biomarkers. For Cohorts 4 through 7, a CSF sample will be taken by single LP at baseline and after 24 weeks dosing, or the last dose if treatment is stopped earlier.

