7.2. Discussion of Design and Control

The study will enroll patients with MCI due to AD, mild AD, or moderate AD with amyloid deposition confirmed by amyloid PET imaging using NIAAA work group consensus guidelines (Albert et al. 2011; McKhann et al. 2011). The broad study population is justified for this study because amyloid pathology is well established before the diagnosis of MCI due to AD and does not differentiate during the later stages of disease. Thus, patients within this spectrum are essentially uniform for the purpose of testing LY3002813 effects on target engagement (Jack et al. 2010). Safety, PK, and PD were assessed in this study population in Study AACC for doses of up to 10 mg/kg. Japanese patients are included in this study to help enable the inclusion of Japanese patients in potential subsequent phases of development.

The single-dose arms in Part A are intended to be used to assess whether target engagement can be achieved after a single dose of 10 mg/kg LY3002813 or greater, given that there was evidence of a robust PD signal after only 3 doses of 10 mg/kg LY3002813. The multiple-dose arms will be used to assess a dose response and a time course of amyloid reduction based on florbetapir scans at baseline and at 12- to 24-week intervals. Twenty-four weeks of dosing in Part B is proposed to approximate the maximum duration of dosing leading to amyloid reduction in Study AACC; amyloid scans at 12 weeks and 24 weeks will be used to assess the time course of amyloid removal and identify whether shorter treatment duration (12 weeks) is sufficient. Sustainability of amyloid reduction after completion of 24 weeks of dosing will be assessed by florbetapir PET at 36, 48, and 72 weeks. The higher dose and more frequent dosing (Q2W) may reduce the incidence of immunogenicity identified in Study AACC. If a 12- or 24-week dosing duration is sufficient for amyloid removal, then the risks of immunogenicity and infusion reactions will potentially be limited to that treatment period. Chronic high-dose treatment (Q4W for up to 72 weeks) in Part C will assess the time course of the maximal PD effect and the opportunity to treat until maximum amyloid removal.

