11.1. Determination of Sample Size

Up to approximately 150 patients may be enrolled so that approximately 72 patients complete the study. Cohorts 1, 2, and 3 are each planned to have approximately 8 patients (6 LY3002813; 2 placebo) complete the study. Cohorts 4 and 5 are each planned to have approximately 12 patients (9 LY3002813; 3 placebo) complete the study. Also, Cohorts 6 and 7 are each planned to have approximately 12 patients (9 LY3002813; 3 placebo) complete the study.

The sample size is customary for studies evaluating safety, PK, and/or PD parameters; at the conclusion of the trial, confidence intervals for PK, PD, and cognition endpoints may be computed in order to evaluate the precision of the estimates where appropriate. Based on prior Lilly clinical trials, 6 patients randomized to each LY3002813 dose and placebo provide over 90% power to detect at least a **CCI** mean SUV_r reduction of a dose compared to that of placebo without multiple comparison adjustment. Based on Fixed and Adaptive Clinical Trial Simulator simulations, there is over 90% success rate that at least 1 LY3002813 dose separates from placebo with a success criterion of $\Pr(\text{mean SUV}_r \text{ reduction of LY3002813 dose} < \text{mean SUV}_r \text{ reduction of placebo}) > \text{CCI}$. If more patients are needed to determine safety, target engagement, PK, dosing, and/or race differences, then up to a total of 10 additional patients may be added.

Patients who are randomized but who do not complete the 12-week safety and PET assessments may be replaced.

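### The SUVr analysis specifies contrasts against placebo only and stops at Week 48, so it gives no interval for the protocol's dose-response and durability questions

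*SAP*

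**What the plan says.** **Questions the protocol asks.** Protocol 7.2: "The multiple-dose arms will be used to assess a dose response and a time course of amyloid reduction". Protocol 7.1: "the later scans are aimed to assess sustainability of amyloid reduction after completion of dosing in Parts A and B". That section schedules scans at baseline and Weeks 12, 24, 36, 48 and 72, and 7.2 names Weeks 36, 48 and 72 as the sustainability scans for Part B. Section 5.2 lists, among five items that would support further development, "persistence of amyloid removal after completion of dosing".

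**Analysis the SAP plans.** Section 4.2.5.1 fits an MMRM with treatment, visit and their interaction to change and percent change in composite SUVr. The visits are Weeks 12, 24, 36 and 48, and early-discontinuation scans are mapped to the nearest of those four. The primary comparison is LY3002813 against placebo at the last PET visit. For output: "A table of the LSmeans per dose group with associated p-value contrast to placebo will be constructed". The section also plans a plot of LSmeans with intervals by visit and dose group, summary tables, counts of patients with SUVr below 1.2, and optional Bayesian posterior probabilities and credible intervals against placebo. Exposure-imaging analyses in 4.2.5.1, 4.2.5.3 and 4.2.6 are optional.

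**Not stated anywhere.** No contrast of 20 with 10 mg/kg, of Q2W with Q4W, or of a late scan with the end-of-dosing scan is given for SUVr. Nor is there a rule for pooling placebo in the SUVr model. SAP 4.2.3 combines placebo within Parts A, B and C, but for the baseline table.

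**The concern.** Two regimens that each differ from placebo have not thereby been compared with each other. Setting two p-values against placebo side by side is not an estimate of dose response. Likewise, a late scan that still differs from placebo does not show that removal persisted, because a large effect can lose much of its size and stay significant.

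The last PET visit is also an uneven basis for comparing regimens. On the protocol's schedules it is Week 24 for Cohort 3, 48 weeks after the end of dosing for Part B, and the end of the 72-week dosing period for Part C.

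At stake is whether the report contains a prespecified estimate, with its uncertainty, of how dose and schedule affect amyloid removal and of how much removal is retained. Without one, such comparisons would be chosen after the results are seen.

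**Working it through.** **1. Week 72.** Protocol 7.1 and SAP 3.4 both list a Week 72 amyloid scan. The SAP uses Week 72 for cognition (4.2.5.2) and for MRI volumes and tau PET (4.2.5.1). Only the SUVr visit list and the early-discontinuation mapping stop at Week 48. The SAP (December 2015) predates the current protocol (December 2017), but that does not explain the omission, since the SAP's own design summary includes Week 72.

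**2. The plan's power figure.** The protocol synopsis states: "6 patients randomized to each LY3002813 dose and placebo provide over 90% power to detect at least a 17% mean florbetapir SUVr reduction", "without multiple comparison adjustment". SD, alpha and sidedness are not given, so the figure cannot be recomputed. Assuming two-sided 0.05 and a t-test of 6 against 6, 17 points has at least 90% power if the SD of percent change is at most about 8.2 points (power 99.3% at SD 6, 91.1% at SD 8). I therefore use an assumed SD of 4 to 8. Simple t calculations stand in for the MMRM.

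**3. Dose against dose.** Inputs: 9 active patients in each of Cohorts 4 to 7 (Protocol 11.1).

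- One pair, 9 v 9: SE = SD × √(2/9), or 1.89 at SD 4 and 3.77 at SD 8. With t(16) = 2.12, the 95% half-width is 4.0 to 8.0 points.
- Averaged over schedule, 18 v 18: SE = SD × √(2/18), or 1.33 to 2.67.
- Power to detect a 5-point difference, 9 v 9: 70% at SD 4, 38% at SD 6, 24% at SD 8.

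These are useful estimates but not powered tests.

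**4. Durability against placebo.** For the change between two visits in one nine-patient arm, minus the same change on placebo:

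SE = √[2(1 − ρ)(SD_a²/9 + SD_p²/n_p)]

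Assume active SD 8. Placebo n at Week 72 is 6 if pooled within Part B (3 + 3). Across all cohorts it is at most 16 (2 + 2 + 3 + 3 + 3 + 3), because Cohort 3 ends at Week 24.

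| Placebo SD, n | ρ = 0.6 | ρ = 0.8 | ρ = 0.9 | As if independent (ρ = 0) |
|---|---|---|---|---|
| 4, 16 | 2.55 | 1.80 | 1.27 | 4.03 |
| 8, 16 | 2.98 | 2.11 | 1.49 | 4.71 |
| 8, 6 | 3.77 | 2.67 | 1.89 | 5.96 |

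The first three results columns need the between-visit covariance. The planned plot shows separate intervals per visit, from which a reader can recover only the last column.

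**5. Durability within arm.** Half-width = t(8) × SD × √[2(1 − ρ)]/√9, with t(8) = 2.306. At ρ = 0.7 this is 2.4 points at SD 4 and 4.8 at SD 8.

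**6. A late placebo contrast after half the effect is lost.** Suppose 17 points at end of dosing has fallen to an observed 8.5, with t = 8.5/[SD × √(1/9 + 1/n_p)].

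| SD (both arms) | p, 6 placebo | p, 16 placebo |
|---|---|---|
| 4 | 0.0014 | 0.00004 |
| 6 | 0.019 | 0.0025 |
| 8 | 0.065 | 0.018 |

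In five of six settings the late contrast is below 0.05 although half the removal has gone. The p-value depends mainly on SD and placebo pooling, not on persistence.

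**The case against.** The strongest reply is that the SAP answers its stated primary objective, the effect on plaque load, and dose against placebo is the right contrast for that. It plans more than p-values: LSmeans with intervals by visit and dose group through Week 48 show the time course, and a reader can roughly rebuild a difference between two independent arms from them. Exposure analyses may use modelling. Both documents call the PD analyses exploratory and changeable without a protocol amendment. All of this stands. A reader might infer that the plan reports only p-values or cannot address these questions at all; the documents do not support that.

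A reader might also infer that every multiple-dose arm is bound to give a tiny p-value. That forecast needs an SD, a placebo pool and a true effect that the documents do not fix. At an observed 17 points, p for 9 active against 3 placebo runs from 0.00008 (SD 4) to 0.011 (SD 8.2); against all 18 placebo it runs from 1.4 × 10⁻¹⁰ to 0.00003. Nor does Study AACC make the placebo contrasts redundant: it went only to 10 mg/kg, dosed about monthly.

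Finally, patients are randomised within cohort, and Cohorts 5 and 7 open only after some safe dosing in Cohorts 4 and 6. Comparisons across cohorts are therefore not randomised and are partly confounded with time. That limits what they can show. It is a reason to label them descriptive, not to leave them unspecified.

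What the reply does not meet is durability. Visit-wise intervals omit the covariance that a within-patient change needs, and Week 72 is absent from the model.

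**Conclusion.** The concern holds in this form: SAP 4.2.5.1 specifies no dose-versus-dose or end-of-dosing-to-late-scan estimate with an interval for SUVr, and its model leaves out the scheduled Week 72 scan. The reading of the documents needs no assumption. The sizes do. At an assumed correlation of 0.8 and active SD of 8, the durability contrast against placebo has SE 1.8 to 2.7 points, depending on placebo SD and pool, against 4.0 to 6.0 if visits are treated as independent. A 9 v 9 dose contrast has a 95% half-width of about 4 to 8 points for SD 4 to 8. The change is worth making, but its absence does not undermine the primary comparison with placebo.

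**What to change.** In SAP 4.2.5.1:

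1. Add Week 72 to the MMRM visits and to the early-discontinuation mapping.
2. State how placebo is pooled across cohorts for SUVr, and give each regimen its own treatment level in a model that covers Parts B and C together.
3. From that model, report estimates with 95% confidence intervals for:
   - (a) 20 v 10 mg/kg at Week 24, within Q2W (Cohort 5 v 4), within Q4W (7 v 6), and averaged;
   - (b) Q2W v Q4W at the same dose at Week 24;
   - (c) change from Week 24 to Week 72 in Cohorts 4 and 5, and from Week 12 or 24 (choose one in advance) to Week 72 in Cohorts 1 and 2, within arm and against placebo;
   - (d) each dose-minus-placebo difference.
4. Label (a) and (b) as descriptive, giving the within-cohort randomisation and staggered opening as the reason.

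Week 24 suits (a) and (b) because Parts B and C are both still within their dosing periods up to that scan. It is also only the second post-baseline scan, so Part C's switch to placebo after two consecutive low scans should not yet have altered exposure.

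The cost is a revised visit list, a few contrast statements and one table. No new data or protocol amendment is needed. The downside is a little more analysis and some wide intervals.

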7.1.4. Part B: 24-Week Q2W Multiple Dose Cohorts (Cohorts 4 through 5)

Safety, PK, and PD will be assessed in Cohorts 4 and 5, during and after multiple doses of LY3002813 or placebo have been administered Q2W for 24 weeks. The planned doses are 10 and 20 mg/kg IV with 12 patients (9 LY3002813; 3 placebo) planned to be enrolled in each cohort. Cohort 4 (10 mg/kg IV Q2W for 24 weeks) will be initiated after review of the safety (at least 1 week after dosing) and PK data (complete Day 29 visit) from at least 4 patients receiving LY3002813 and 1 receiving placebo in Cohort 1. Cohort 5 (20 mg/kg IV Q2W for 24 weeks) will only be initiated after review of the safety and PK data (at least 4 weeks after dosing) from Cohort 2 in at least 4 patients receiving LY3002813 and 1 receiving placebo, and after confirmation that at least 2 patients have been dosed safely with LY3002813 at least 3 times each in Cohort 4. Safety and PD will be assessed at regular intervals for approximately 48 weeks after completion of 24 weeks of dosing with LY3002813 ([Attachment 1](#)).

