7.1.5. Part C: Chronic, 72-Week Q4W Multiple Dose Cohorts (Cohorts 6 and 7)

Safety, PK, and PD will be assessed in Cohorts 6 and 7 during and after multiple doses of LY3002813 or placebo have been administered Q4W for up to 72 weeks, or when the LY3002813-induced reduction in amyloid measured by florbetapir reaches the maximum reduction (defined as SUVr <1.1 for 2 consecutive scans) (Joshi et al. 2015). The planned doses are 10 and 20 mg/kg IV with 12 patients (9 LY3002813; 3 placebo) planned to be enrolled in each cohort. Cohort 6 (10 mg/kg IV Q4W) and Cohort 7 (20 mg/kg IV Q4W) may proceed, in parallel with Cohorts 4 and 5, respectively. In addition, Cohort 7 will only be initiated after confirmation that at least 2 patients have received at least 2 doses each of LY3002813 safely in Cohort 6. The maximum dose of 20 mg/kg will not be exceeded. If a patient is deemed to be amyloid negative by florbetapir PET before completion of 18 months' dosing (SUVr <1.1 for 2 consecutive scans), the patient will receive placebo infusion for all subsequent visits and continue the Part C visit schedule, including assessment of sustained amyloid reduction at the scheduled PET scan assessments. Safety, PK, and PD will be assessed for all patients at regular intervals for approximately 12 weeks after completion of 72 weeks of dosing with LY3002813 ([Attachment 1](#)).

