11.2.5.1. Imaging Analyses

Statistical assessment of the SUVr will be analyzed by a mixed model repeated measure (MMRM). The planned analyses is an MMRM using at least compound symmetry covariance structure with fixed effects of treatment doses (LY3002813 and placebo), study visit, and interaction between treatment and visit. A baseline covariate adjustment may be used. The primary comparison is between LY3002813 and placebo for change from baseline in composite SUVr or percent change in composite SUVr at last PET imaging visit. This analysis may be repeated for SUVrs in individual brain regions if needed.

In addition to the MMRM analysis, a Bayesian posterior probability may be computed for each LY3002813 dose compared to placebo. For each dose, the credible interval will be computed for each dose relative to placebo.

Changes in volume (including, but not limited to, whole brain, ventricle, and hippocampus), brain tissue microstructure, and functional connectivity in brain networks captured by MRI over the course of the study will be explored; exploratory evaluation of whole brain and anatomically localized structural and functional changes will be summarized. MRI will be obtained every 12-24 weeks; therefore, an MMRM may be conducted fitting treatment and study visit as fixed effects.

Additionally, the relationship between LY3002813 serum exposure and imaging endpoints may be explored graphically or by a modeling approach.

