#### 4.2.7.3. Evaluation of Immunogenicity (for Large Molecules)

As part of the secondary study objective, Antibody drug formation will be summarized over time for each IV dose group. An MMRM will be done fitting IV dose, study visit, and interaction between study visit and dose as fixed effects and the dependent variable as the change from baseline in antibody formulation following dosing of LY3002813. The relationship between the presence, absence or level of ADAs and number of IV drug infusion reaction AEs, PK estimates of exposure, PD measurements of amyloid SUVR. These associations may be assessed using simple pairwise correlations and pairwise graphical relationship. These relationships may also be described using a modeling approach, if appropriate.

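### The MRI-volume MMRM omits treatment-by-visit, so it gives each dose one constant effect and cannot show whether a volume effect grows, holds or wanes

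*SAP*

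**What the plan says.** SAP section 4.2.5.1 sets the schedule for volumes, "Magnetic resonance imaging volumetric assessments will be obtained at baseline, 24 weeks, 48 weeks, and 72 weeks as applicable", and then the model: "An MMRM will be constructed by fitting treatment and study visit as fixed effects". The responses are changes in whole brain, ventricle and hippocampal volume. The section gives no covariance structure, baseline covariate, time point or contrast for these volumes. Protocol section 11.2.5.1 lists the same two effects, as an option: "an MMRM may be conducted fitting treatment and study visit as fixed effects".

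The SAP's other three mixed models are fuller:

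- SUVr (section 4.2.5.1): "fixed effects of treatment doses (LY3002813 and placebo), study visit, and interaction between treatment and visit".
- Cognition and function (section 4.2.5.2): the same three terms, at the same Weeks 24, 48 and 72.
- ADA (section 4.2.7.3): "An MMRM will be done fitting IV dose, study visit, and interaction between study visit and dose as fixed effects".

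For SUVr the SAP adds that "simplification of the mixed-effects model might be considered if the model fails to converge", and section 4.2.5.2 has a similar fallback for cognition. The MRI model is not described as a simplification of this kind, and no reason is given for assuming a constant effect.

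**The concern.** A model with only treatment and visit main effects forces each dose's difference from placebo to be the same at every visit. That conflicts with the stated interest in how volumes change during the study, and this design gives little reason to expect constancy:

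- Part A is a single dose.
- Part B stops dosing early: "Safety and PD will be assessed at regular intervals for approximately 48 weeks after completion of 24 weeks of dosing with LY3002813" (Protocol section 7.1.4).
- In Part C, "multiple doses of LY3002813 or placebo have been administered Q4W for up to 72 weeks" (Protocol section 7.1.5), with a switch to placebo infusions for patients who become amyloid negative.
- Cohort 3's MRI span is only 24 weeks (Protocol section 10.5.2). It contributes volume data at Week 24 alone, while the other cohorts run to Week 72.

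The coefficient would then be a blend over visits, with weights set by a covariance structure the SAP does not specify for this model. With no time point named, a reader could take it for an end-of-study effect. Cohort 3's coefficient is affected too: the visit effects are shared with cohorts whose effect may change over time, so it is not a clean Week 24 contrast.

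**Working it through.** The plan states no effect size, SD or power for volumes, so there is no figure to reproduce. The check is what the specified model would estimate under stated assumptions.

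**Inputs from the documents.** Planned arms (SAP section 4.1): 6 active and 2 placebo in each of Cohorts 1-3; 9 active and 3 placebo in each of Cohorts 4-7. Pooled placebo is 3×2 + 4×3 = 18. Of these, 16 have all three visits and the 2 from Cohort 3 have Week 24 only.

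**Assumptions.** Complete data at scheduled visits, placebo pooled unless stated, no baseline covariate. Within-patient correlation is compound symmetry (CS) 0.6 unless stated. SDs are equal across visits, or rise 1:1.5:2, or fall 1:0.8:0.6.

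**Formula.** For one dose against placebo, with true differences d = (d24, d48, d72) and within-patient covariance V, the main-effects coefficient has expectation w′d, where w = V⁻¹1 / (1′V⁻¹1). The seven-arm generalised least squares fit, including Cohort 3, was also solved directly.

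**Step 1: different courses, same coefficient.** Under CS with equal SDs, w = (1/3, 1/3, 1/3).

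- Waning (1, 0.67, 0.33): (1 + 0.67 + 0.33)/3 = 0.67.
- Growing (0.33, 0.67, 1): the same sum, 0.67.

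In the seven-arm model with Part B waning, Part C growing and Part A flat at 0.33, Cohorts 4-7 all return 0.667 under CS 0.4, 0.6 and 0.8 and under AR(1) 0.6. If SD rises, the growing arms return 0.301 and the waning arms 1.033, the reverse of their Week 72 order. If SD falls, they return 0.974 and 0.360, close to their Week 72 values of 1 and 0.33.

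**Step 2: coefficient divided by the true Week 72 effect**, when all doses share one course. Where two values are given, the first is the single contrast and the second the seven-arm model.

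| Course | SD | Ratio |
|---|---|---|
| Linear (0.33, 0.67, 1) | equal | 0.667, 0.646 |
| Square-root growth | equal | 0.798, 0.784 |
| Levelling off (0.5, 1, 1) | equal | 0.833, 0.812 |
| Levelling off (0.5, 1, 1), AR(1) 0.6 | equal | 0.792, 0.775 |
| Delayed (0, 0.5, 1) | equal | 0.500, 0.469 |
| Quadratic growth | equal | 0.519, 0.493 |
| Waning (1, 0.75, 0.5) | equal | 1.50, 1.53 |
| Linear | 1:1.5:2 | 0.301, 0.303 |
| Linear | 1:0.8:0.6 | 0.974, 0.954 |

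With rising SDs the weights are about (0.99, 0.12, -0.11), so the coefficient is in effect a Week 24 estimate.

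**Step 3: Cohort 3, true Week 24 effect 0.333.** With linear growth in the other cohorts:

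| Placebo used | Equal SD | SD rises | SD falls |
|---|---|---|---|
| All pooled | 0.561 | 0.312 | 0.785 |
| Part A only | 0.512 | 0.317 | 0.716 |

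With growth in Part C only and every other arm flat at 0.333, Cohort 3 returns 0.419 (pooled placebo, equal SD).

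**Step 4: price of the interaction.** For a 9-patient arm with SD = 1, the pooled coefficient has standard error 0.351 and the Week 72 contrast 0.414. As a check, the simple two-group value is √(1/9 + 1/16) = 0.417. The ratio is 0.414/0.351 = 1.18. It runs from 1.08 (CS 0.8) to 1.30 (CS 0.4), and is 1.24 under AR(1) 0.6. If SD rises 1:1.5:2, it is 0.827/0.401 = 2.06.

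**The case against.** The strongest case is about weight. MRI volume is an exploratory objective, and SAP section 4.2.5 already plans summaries or plots of PD measures by visit. With 6 to 9 active patients per dose, an average over visits is a legitimate and more precise summary. The wording may also be protocol shorthand: Protocol section 11.2.5.3 lists only dose and visit for cognition, and the SAP then added the interaction. All the figures depend on assumed shapes and variances, and the percentages apply only to someone who reads the coefficient as a Week 72 effect, which the SAP never says.

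Most of this stands as a limit on importance. It does not remove the point. Descriptive plots give no model-based contrasts. An average over visits is defensible only if it is named as the target, and here its weights shift with an unspecified covariance. The SAP added the interaction for cognition but not for volumes, so a programmer following the text would leave it out.

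On Cohort 3, two replies have force. Its follow-up was cut by protocol amendment (f), after the SAP was approved, so the gap is partly a matter of an SAP not updated. And in the Step 1 scenario its coefficient is exactly 0.333. That agreement, however, relies on equal and opposite Part B and Part C courses cancelling; with growth in Part C alone it is 0.419. The Cohort 3 distortion is therefore real but conditional, and nearly absent if variances rise over time.

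**Conclusion.** The concern holds. Followed as written, the MRI-volume model cannot distinguish a sustained, growing or waning effect, and the SAP gives no reason for departing from its other three mixed models.

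The size cannot be fixed from the documents. Read as a Week 72 effect, with equal variances, linear growth is understated by 33-35%, levelling-off growth by 17-23% and delayed growth by about half; waning to half is overstated by 50-53%. Under linear growth, the understatement is about 70% if SD rises 1:1.5:2 and only 3-5% if it falls 1:0.8:0.6. The identical coefficients in Step 1 need equal variances; under other structures different pairs of courses coincide.

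The by-visit descriptive summaries and the primary SUVr analysis are unaffected. This is a change that should be made, of modest importance.

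**What to change.** Amend the MRI paragraph of SAP section 4.2.5.1 to fit treatment, visit, treatment-by-visit and baseline volume. Report the Week 24 contrast with placebo for all cohorts, and the Week 72 contrast for Cohorts 1, 2 and 4-7. Extend the SUVr model's simplification fallback to this model. If a constant effect really is intended, state why and say what the coefficient estimates.

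The edit is one line, and SAP section 4.2.5 says changes to these analyses need no protocol amendment. The interaction adds 12 fixed-effect parameters (2 for each of the 6 dose arms with three visits; none for Cohort 3). The price is the loss of precision in Step 4: a Week 72 standard error 1.08 to 1.30 times the pooled one with constant variance, and about double if SD rises as assumed.
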